5.6.6 Microincentives

Microincentives are increasingly being used to support users for their time and effort in using assistive applications in clinical trials and real-world settings.²⁸ Participants in the intervention arm will be provided \$0.50 each day the AiCure system is used for dosing. As participants in the control condition will not be using the AiCure system, they will be asked to track the number of steps they take each day using a fitness app on their smartphone and will be provided \$0.50 each day they send a screenshot from this app via text message to a secure research portal. Participants may also choose a different activity to track each day (e.g. number of hours they slept the night before) and text this information to the study team in the same manner. Intervention participants will be reimbursed every 2 weeks via an electronic payment system linked to the DOT Diary app (based on use of the app during that 2 week period) or receive a lump-sum payment at their next study visit.

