2.0 Longitudinal Pilot Study Objectives

2.1 Primary Objectives

- 1. To assess the effect of DOT Diary on PrEP adherence as measured by TFV-DP in DBS among YMSM initiating PrEP
- 2. To evaluate the concordance of TFV-DP and FTC-TP in DBS with adherence measured by DOT Diary
- 3. To assess the acceptability and ease of use of DOT Diary over a 24 week period

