2.2 Secondary Objectives

- 1. To assess PrEP coverage of sexual acts (prevention-effectiveness adherence) as measured by DOT Diary in the intervention arm
- 2. To evaluate the daily use of the DOT and diary components of the DOT Diary through 24 weeks of follow-up

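### The randomised contrast is DOT Diary plus a daily payment tied to dosing through the app, but the objectives and the SAP describe it as DOT Diary alone

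*Protocol*

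**What the plan says.** Section 5.6.6 of the protocol sets the payment rule. The intervention arm earns USD 0.50 for "each day the AiCure system is used for dosing". Controls earn USD 0.50 for "each day they send a screenshot from this app via text message to a secure research portal", the app in question being a step counter. The rule then widens: "Participants may also choose a different activity to track each day", with sleep given as an example. Intervention payments are made every two weeks, "based on use of the app during that 2 week period", or as a lump sum at the next visit. The stated rationale is to "support users for their time and effort in using assistive applications in clinical trials and real-world settings".

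Primary objective 1 (section 2.1) is "To assess the effect of DOT Diary on PrEP adherence as measured by TFV-DP in DBS among YMSM initiating PrEP". Section 5.1 describes randomisation to receive the app or not. Section 5.2 defines DOT Diary as a smartphone app and lists its functions; payment is not among them. Section 5.6.2 calls the control condition PrEP alone. The SAP's first primary objective estimates the average effect of assignment to DOT Diary on TFV-DP at or above 700 fmol/punch. Its section on treatment effect mechanism looks at app time, diary time and sexual risk, and does not mention payment.

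Secondary objective 2 (section 2.2) is "To evaluate the daily use of the DOT and diary components of the DOT Diary through 24 weeks of follow-up".

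**The concern.** Matching the daily rate controls for receiving money. It does not control for what the money rewards. One arm is rewarded for dosing through the app, the other for a task unrelated to PrEP. TFV-DP in dried blood spots reflects doses taken, so a reward linked to dosing bears on the behaviour behind the primary outcome.

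If the report concludes that DOT Diary raised adherence, it credits the app with whatever the payment contributed. The same holds for usage. A high rate of daily DOT use would describe use under payment and might not carry over to a setting without it. A comparison of DOT use with diary use would also be uneven, because only the first is described as paid.

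A smaller gap lies in the control rule. Nothing stops a control from choosing pill-taking as the tracked activity. That participant would then be paid for daily self-monitoring of PrEP, which would narrow the contrast.

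**Working it through.** **1. What each arm receives.**

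| Component | Intervention | Control |
|---|---|---|
| PrEP and adherence counselling | yes | yes |
| DOT Diary app | yes | no |
| USD 0.50 per day on offer | yes | yes |
| What earns it | using the app for dosing | step count or another chosen activity |

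The arms differ in two rows, the app and what earns the payment. The two always go together: no group has the app without dosing-linked payment, and none is assigned that payment without the app. No analysis of these data can separate them.

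**2. Amount at stake.** Follow-up is 24 weeks × 7 = 168 days. The maximum is 168 × USD 0.50 = USD 84, or USD 3.50 per week and USD 7.00 per two-week cycle. The control maximum is the same if controls report every day. What differs is the amount that depends on dosing: up to USD 84 against nothing, unless a control chooses pill-taking.

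**3. The plan's own power figure.** Inputs from protocol sections 5.3 and 6.2.1: arms of 67 and 33, control proportion 60%, ICC 0.69, an average of 3.59 blood spots per participant, two-sided 5% test. The blood-spot average is given for the intervention arm and is applied here to both arms.

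- Variance factor: (1 + 2.59 × 0.69) / 3.59 = 0.776.
- Effective sizes: 33 / 0.776 = 42.5 and 67 / 0.776 = 86.3.
- At 60% against 83%, the pooled proportion is 0.754. The null standard error is √(0.754 × 0.246 × (1/42.5 + 1/86.3)) = 0.0807.
- The alternative standard error is √(0.24/42.5 + 0.1411/86.3) = 0.0853.
- z = (0.23 − 1.96 × 0.0807) / 0.0853 = 0.84, giving power of 80.0%.

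The stated minimum detectable difference of 23 points is reproduced and is not in dispute.

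**4. Illustration of the labelling problem.** The documents give no effect size for payment, so the first column below is assumed. Effects are taken as additive and the control payment as having no effect on adherence. For an app with no effect of its own, the standard error is √[0.776 × (0.24/33 + p(1 − p)/67)], where p = 0.60 + payment effect. At 10 points this is 0.0899, so z = 0.10 / 0.0899 = 1.11 and the two-sided chance of significance is about 20%.

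| Assumed payment effect (points) | Chance of a significant result if the app does nothing | App's part of a 23-point total |
|---|---|---|
| 0 | 5% | 23 |
| 3 | 6% | 20 |
| 5 | 8–9% | 18 |
| 10 | 20% | 13 |
| 15 | 40% | 8 |

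These rows show how the conclusion depends on an unknown. They are not estimates for this trial.

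**5. Usage.** Section 5.6.6 ties payment to dosing use. The later wording about two-week reimbursement speaks of app use more generally, but it describes when payment is made and does not set out a separate payment for diary entries. Secondary objective 2 therefore measures a paid component and one for which no payment is described. The SAP's intention-to-treat and per-protocol denominators deal with dropout, not with this.

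**The case against.** The strongest reply is that the comparison is sound as randomised. The SAP targets the effect of assignment, and assignment includes whatever comes with the app. Section 5.6.6 presents microincentives as common in practice and allows payment through a system linked to the app, so they can be read as part of delivery. Controls have a matched rate and a daily phone task, and the sum is small. All of this stands, and it reduces the point to what the intervention is called. It does not remove the point, because section 5.2, the objectives and the SAP never include the payment.

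Four stronger readings are tempting and are not supported:

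- That primary objective 1 cannot be answered. The package effect is validly estimated; only its attribution to the app alone fails.
- That the intervention arm is paid for confirmed ingestion. The trigger is use of the system for dosing. The protocol does not say that payment requires confirmation; section 5.6.3 mentions overrides, and the SAP separates confirmed from self-reported pill-taking. A dose taken outside the app earns nothing.
- That payment distorts app–DBS concordance through feigned dosing. The protocol has automated flagging, human review and staff contact, and DBS is an independent comparator. No such effect is shown.
- That a go/no-go decision rests on this result. Section 1.0 speaks of evaluating and refining the app in preparation for a larger trial and states no such rule.

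A control choosing pill-taking is also only a possibility. The examples given are steps and sleep.

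**Conclusion.** The point holds as a mismatch between the intervention delivered and the intervention named. The trial can support a statement about DOT Diary with a USD 0.50 daily microincentive for dosing use. It cannot support one about the app alone, either for TFV-DP or for daily DOT use.

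The asymmetry follows directly from section 5.6.6, and its ceiling is USD 84 per intervention participant. The size of any payment effect cannot be derived from the documents; it may be close to nil. The illustrative probabilities depend on the assumed payment effects and on additivity. The power calculation and the validity of the randomised comparison are unaffected.

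**What to change.** 1. In protocol section 5.2, primary objective 1, secondary objective 2 and the SAP, define the intervention as DOT Diary with a USD 0.50 microincentive for each day the app is used for dosing. State that neither the adherence effect nor the usage rate will be attributed to the app alone.
2. In section 5.6.6, state that controls may not choose medication-taking or sexual activity as the tracked activity, so that the control payment cannot become paid PrEP self-monitoring.

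The cost is two short text changes and a narrower claim. Design, sample size and budget stay as they are.

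Paying intervention participants for any daily app check-in is an optional design alternative, not a required correction. It would remove the link to dosing but would still pay only one arm to open an adherence app. It could also pay for diary opening, which secondary objective 2 bears on, and the documents describe no app function for reporting that no dose was taken.

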5.6.7 Toxicity Management

The site investigator has the discretion to hold TDF/FTC at any time if s/he feels that continued medication use would be harmful to the participant or would interfere with treatment deemed clinically necessary according to the judgment of the investigator. Clinical or laboratory abnormalities that require follow-up will be documented and the clinical provider will contact the participant to schedule an interim visit for follow-up and/or repeat laboratory testing. All participants reporting an adverse event will be followed clinically until the occurrence resolves (returns to baseline grade, defined as grade at enrollment) or stabilizes, or until an effective referral to local health care providers is accomplished.

5.6.8 Procedures for participants with suspected or confirmed HIV infection

The Protocol Team must be notified of any reactive HIV test result identified at any time after study enrollment. Individuals who have one or more reactive or positive HIV tests at Screening are not eligible to participate in this study. Furthermore, at Screening and Enrollment, individuals with any signs or symptoms consistent with acute (preseroconversion) HIV infection will not be enrolled. Participants who have any reactive or positive HIV test result after enrollment will stop TDF/FTC PrEP and will be referred immediately for HIV primary care and treatment per local clinic guidelines.

Interim contacts and visits (those between regularly scheduled follow up visits) may be performed at participant request or as deemed necessary by the investigator or designee at any time during the study. All interim contacts and visits will be documented in a participant management system or participants' study records and/or applicable Clinical Research Forms (CRFs).

Some interim visits may occur for administrative reasons. For example, the participant may have questions for study staff or wish to provide new contact information. Interim visits at which no data are collected are not documented on CRFs. Other interim contacts and visits may occur in response to Adverse Effects (AEs) experienced by study participants, or loss of study medication. When interim contacts or visits are completed in response to participant reports of AEs, study staff will assess the reported event clinically and provide or refer the participant to appropriate medical care. In the event of loss of study medication, additional TDF/FTC medication may be dispensed to the participant per the discretion of the site investigator, and the protocol team will be notified of this occurrence. If the participant's device is no longer working (lost, broken) or the app is not supported by the participant's device, the study site may supply a provisioned device with the app pre-installed for the participant to use for the remainder of the study.

5.6.10 Early termination of study participation

Participants may voluntarily withdraw from the study for any reason at any time. The site investigator may, withdraw participants before their scheduled termination visit to protect their safety or staff safety, and/or if participants are unable or unwilling to comply with study procedures. Participants also may be withdrawn if the study sponsors, government or regulatory authorities (including the OHRP and US FDA), or site IRB terminate the study prior to its planned end date. Study staff will record the reason(s) for all withdrawals in participants' study records. The week 24 visit procedures should be followed when possible, in the event that a participant chooses to withdraw early from the study.

5.6.11 Risks to participation

Phlebotomy

Venipuncture is sometimes associated with discomfort. Phlebotomy may lead to discomfort, dizziness, bruising, swelling, and rarely, an infection at the venipuncture site.

HIV and STI Testing

Examination and swabbing of the pharynx and rectum can be associated with discomfort. Participants may become embarrassed, worried, or anxious when completing their HIV risk assessment and/or receiving HIV counseling. They also may become worried or anxious while waiting for their HIV and STI test results. Individuals who learn that they have an STI or HIV infection may experience anxiety or depression related to their test results. Trained clinic staff will be available to help participants deal with these feelings.

Sensitive Questions

Participants will be asked questions about their sexual behavior that may make them feel uneasy. Participants do not have to answer any question that they do not want to and can

stop answering the questions at any time. Participants may also become embarrassed, worried, or anxious when being counseled about PrEP.

Confidentiality

Although study sites will make every effort to protect participant privacy and confidentiality, it is possible that participants' involvement in the study could become known to others, and that social harms may result (e.g., because participants could become known as at "high risk" for HIV infection or be thought to be HIV-positive). For example, participants could be treated unfairly or discriminated against, or could have problems being accepted by their families and communities. In addition, we are evaluating a mobile app that captures information about the participant's dosing of PrEP and sexual encounters with partners. Multiple measures have been taken in the app to protect participant confidentiality, including password protection of the app, and blurring and encryption of images prior to electronic transmission. However there is the possibility that this information could become known to others. Study data will be stored using password protected databases and double-locked cabinets will be used to store contact and consent forms, which will have participant identifying information.

HIV Resistance

It is possible that a participant who is taking PrEP and becomes infected with HIV during this study may develop viral resistance mutations to TDF/FTC. Multiple steps will be taken to minimize the risk of drug resistance. HIV testing will be performed at Screening and Enrollment, and then at every follow-up visit (every 6 weeks). Persons with acute viral syndromes that may reflect acute HIV infection will not be eligible for enrollment. If acute HIV infection is suspected after enrollment, the participant will undergo evaluation using tests described in the SSP Manual. These steps should minimize the risk of drug resistance occurrence by identifying HIV infection in its early stages and stopping TDF/FTC. If any participant becomes HIV-infected during the study and develops TDF or FTC resistance, an alternative treatment regimen could be used that is not impacted by resistance to these drugs.

TDF/FTC Side Effects.

TDF/FTC is a FDA-approved drug licensed for the indication of PrEP for HIV prevention. Risks and side effects related to TDF/FTC include the following:

- Gastrointestinal intolerance (such as nausea, abdominal pain, diarrhea, or vomiting)
- Flatulence
- Headache
- Sleep disturbance
- Rash
- Redistribution/accumulation of body fat. This has been observed in HIV-infected patients receiving combination antiretroviral therapy. The mechanism and long-term consequences of these events are currently unknown. A causal relationship has not been established. These effects are not expected in this study involving a brief exposure to antiretroviral drug.

Rare, but serious side effects include:

DOT Diary Longitudinal Pilot Protocol

- Lactic acidosis/severe hepatomegaly with steatosis
- Renal impairment, including cases of acute renal failure and Fanconi's syndrome (renal tubular injury with severe hypophosphatemia)

- Increase in bone metabolism leading to osteopenia or osteomalacia
- Hypersensitivity reaction

5.6.12 Benefits to the subject or future benefits

As part of study participation, participants will be provided up to 9 months of free TDF/FTC PrEP and assistance with PrEP navigation to establish ongoing PrEP access. There may be benefits for future PrEP trials or PrEP use, if information gained results in an improved aDOT app.

6.0 Data management and analysis

6.1 Data management

CASI data will be collected online using Qualtrics and stored in password-protected databases. The aDOT app will require a unique log-in and password and secure connections will be utilized as a way to protect confidentiality. Participants will be assured that the information they provide will be managed with the highest standards of confidentiality. All study staff will be trained in Good Clinical Practice (GCP) and will have received additional training about maintaining confidentiality.

The AiCure smartphone app makes a real-time determination of whether the participant has properly administered their medication, providing reminders and encouraging following proper procedures to ensure medication ingestion as prescribed. Study participants will receive a medication reminder at a time within a predefined window. This notification reminds participants to take their medication dose while using the AiCure smartphone app. Participants will follow a series of prescribed steps in front of the front-facing webcam to visually confirm their ingestion of the medication. The application on the smartphone will make an automated determination of whether the patient has properly taken their medication at the prescribed time. There is no need for study personnel to review the administration, nor would study personnel need to be available at the time the participant takes their medication. The amount of guidance that the device provides to the participant is automatically reduced as the participant becomes more proficient at using the application.

Study personnel will have access to real-time data on a browser-based dashboard. Study personnel may switch on automated notifications (notifications are based on adherence thresholds) and will receive regular participant and site updates (dosing and intervention summaries, site performance data, and week on week adherence rates). In addition to dosing data, the platform will automatically flag behavioral events for further review that may be indicative of a participant intentionally not taking the medication, or 'feigning' adherence. If deceptive behavior is confirmed by human review, study personnel are notified. Based on the data, study staff will determine whether to follow up with a participant and select a method for intervention. If the intervention is conducted via the browser-based dashboard (by phone, SMS text, or request for in-clinic visit), the intervention will be logged. Intervention will consist of non-judgmental contact with the participant, such as asking if they are having trouble using the mobile app or taking their medication as directed. At the end of the study, all raw data logged on the AiCure platform will be distributed to study personnel for analysis.

On the participant side, after dosing is completed, video data are encrypted and transmitted to a secure centralized location for further analysis. Once received at the

centralized location, the data are then removed from the device (store and forward). The captured data and video are reviewable through a roles and rules restricted system ensuring privacy of the information, allowing access to the data by study team members at the research sites. Video data captured by the aDOT platform will only be available to AiCure personnel and will be analyzed for proper medication administration. Individuals outside the clinical sites will not know the identity of the study participants and will be destroyed on or before January 1, 2021. The system is compliant with the Health Insurance Portability and Accountability Act (HIPAA), which protects the privacy and security of healthcare information.

Phone numbers of the participants may also be collected and stored in an encrypted manner. Storing the phone numbers will allow for direct communication with participants, including automated messaging from the aDOT platform and contact by study personnel or other monitoring personnel. At no time is the phone number visible to study personnel or monitoring personnel. Individuals outside the clinical sites will not be provided with participant names, nor will they be given access to participant medical records. Phone numbers will not be used by AiCure for any non-study purpose.

Partner nicknames and ratings entered in the sexual diary will be stored secure servers for back-up purposes only and will not be used for any purpose, including research. Clinical site staff will not have access to partner-specific information such as nickname or ratings.

Audio-recorded qualitative interviews at week 24 will be recorded onto digital media using a portable recorder that records directly into computer readable format and can be transferred from the recorder and stored in an encrypted volume that is then stored on a secure computer or burned on a DVD which will be stored in a locked cabinet. The data will be transferred via USB cable to a password-protected, encrypted volume created on a laptop computer. Only study personnel will have access to the password. A copy of the encrypted volume would be stored on secured servers at one of the research institutions for study team members at different research sites to access. The encrypted volume will be opened (mounted) only when it is being used for analysis purposes. At all other times, the encrypted volumes containing the data will remain closed (dismounted) and thereby encrypted. Because the data are stored in an encrypted format, the risk of unauthorized access is very low.

